### 3.2 Exclusion Criteria

Any potential subject who meets any of the following criteria will be excluded from participating in the study.

1. Subject has a diagnosis of primary amyloidosis, monoclonal gammopathy of undetermined significance, or smoldering multiple myeloma. Monoclonal gammopathy of undetermined significance is defined by presence of serum M-protein  $< 3$  g/dL; absence of lytic bone lesions, anemia, hypercalcemia, and renal insufficiency related to the M-protein; and (if determined) proportion of plasma cells in the bone marrow of 10% or less. Smoldering multiple myeloma is defined as asymptomatic MM with absence of related organ or tissue impairment end organ

damage

2. Subject has a diagnosis of Waldenström's disease, or other conditions in which IgM M-protein is present in the absence of a clonal plasma cell infiltration with lytic bone lesions
3. Subject has prior or current systemic therapy or SCT for MM, with the exception of an emergency use of a short course (equivalent of dexamethasone 40 mg/day for a maximum 4 days) of corticosteroids before treatment.
4. Subject has a history of malignancy (other than MM) within 5 years before the date of enrollment (exceptions are squamous and basal cell carcinomas of the skin and carcinoma in situ of the cervix, or malignancy that in the opinion of the investigator, with concurrence with the sponsor's medical monitor, is considered cured with minimal risk of recurrence within 5 years).
5. Subject has had radiation therapy within 7 days of enrollment.
6. Subject has had plasmapheresis within 28 days of enrollment.
7. Subject is exhibiting clinical signs of meningeal involvement of MM.
8. Subject has known chronic obstructive pulmonary disease (COPD) (defined as a forced expiratory volume [FEV] in 1 second <60% of predicted normal), persistent asthma, or a history of asthma within the last 2 years (intermittent asthma is allowed). Subjects with known or suspected COPD or asthma must have a FEV1 test during screening.
9. Subject is known to be seropositive for history of human immunodeficiency virus (HIV) or known to have active hepatitis B or hepatitis C.

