### **5. TREATMENT PLAN**

#### **5.1 Treatment Regimen**

Carfilzomib, lenalidomide, dexamethasone, and isatuximab will be administered on a 28-day treatment cycle. All subjects will perform stem cell collection after 4 cycles of therapy.

For patient undergoing upfront stem cell transplant (SCT):

4 cycles of therapy followed by stem cell collection, high-dose chemotherapy, and autologous SCT followed by 2 additional cycles of therapy then maintenance.

For patients deferring SCT following collection:

4 cycles of therapy followed by stem cell collection followed by 4 additional cycles of therapy then maintenance.

Carfilzomib 56 mg/m^2 IV on Days 1, 8, 15

Lenalidomide 25 mg orally (po) on Days 1-21

Isatuximab 10 mg/kg IV Q1 week for 8 weeks, then Q2 weeks for 16 weeks, thereafter Q4 weeks

Dexamethasone 20 mg po will be administered day of and day after all doses of carfilzomib (Days 1, 2, 8, 9, 15, and 16) and isatuximab (Cycles 1 and 2 Days 22 and 23). The dexamethasone 20 mg oral or IV dose administered as a preinfusion medication on isatuximab infusion days (Days 1, 8, 15, 22) replaces the oral dexamethasone dose for that day.

\*All subjects with receive carfilzomib 20 mg/m^2 on Day 1 Cycle 1

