## 5.2 Pre-Treatment Criteria

A new cycle of treatment may begin on the scheduled Day 1 of a new cycle if the following criteria are met within 24 hours of Day 1:

- ANC  $\geq 1,000/\text{mm}^3$  (growth factor support is permitted during cycles with the exception of Cycle 1 Day 1 (C1D1); it is allowed on the same day as treatment administration).
- Platelet count  $\geq 50,000/\text{mm}^3$  (platelet support is permitted during cycles of treatment; it is allowed on the same day as treatment administration, including C1D1).
- Any lenalidomide-related allergic reaction/hypersensitivity or sinus bradycardia/other cardiac arrhythmia AE that may have occurred has resolved to < Grade 1.
- Any other lenalidomide, carfilzomib, or isatuximab-related adverse event that may have occurred has resolved to <Grade 2.
- Herpes zoster lesions, if present, are dry.

If these conditions are not met on Day 1 of a new cycle, the subject will be evaluated weekly and a new cycle of therapy will not be initiated until the toxicity has resolved as described above. The maximum amount of time that treatment may be held for these toxicities to resolve is 3 weeks. If drug is held for more than 3 weeks due to toxicity, the patient is to discontinue all study treatment and enter the survival follow-up phase of the study.

For intra-cycle dosing on days where laboratory studies are scheduled, the following criteria must be met:

- Platelet count  $\geq 30,000$  (platelet transfusion support is permitted to meet criteria)
- Absolute neutrophil  $\geq 500/\text{mm}^3$  (growth factor support is permitted during cycles with the exception of Cycle 1 Day 1 (C1D1); it is allowed on the same day as treatment administration).

Intra-cycle dose modifications for all drugs will be allowed based on toxicity and according to dose modifications outline in Section 6.1, Table 9.

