**Table 10. Additional Carfilzomib Dose modifications and Safety Measures:**

Hepatic Impairment
 
Mild to moderate liver dysfunction defined as 2 consecutive values at least 28 days apart, of:
 
-Total bilirubin (>33%) > 1x ULN or <3x ULN OR
 
-An elevation of AST and/or ALT with normal bilirubin
	
-25% dose reduction. Dose may be re-escalated if liver function tests return to normal and drug-induced hepatotoxicity is excluded.
 
-Hold carfilzomib until resolution to baseline. Resume with a 25% dose reduction if drug-induced hepatotoxicity is excluded. Monitor bilirubin and direct

---	---

-Grade 3 elevation in total bilirubin
 
-Drug-induced hepatotoxicity (attributable to carfilzomib)
	
bilirubin weekly.
 
-Upon resolution of total bilirubin to normal, resume carfilzomib doing with 25% dose reduction if drug-induced hepatotoxicity is excluded.
 
-Discontinue carfilzomib

Posterior Reversible Encephalopathy Syndrome (PRES)
	
If PRES is suspected, hold carfilzomib, Consider MRI for onset of visual or neurological symptoms suggestive of PRES. If PRES confirmed, permanently discontinue carfilzomib. If PRES excluded, carfilzomib administration may resume at same dose if clinically appropriate.

Thrombotic Microangiopathy (TMA)
	
If the diagnosis is suspected, hold carfilzomib and manage per standard of care including plasma exchange as clinically appropriate. If TMA confirmed, permanently discontinue carfilzomib. If TMS excluded, carfilzomib can be restarted.

Contraception/Female
	
Females of child-bearing potential and/or their male partners should use effective contraception methods or abstain from sexual activity during and for 30 days after treatment with carfilzomib.

Contraception/Male
	
Males and/or their female partners should use effective contraceptive methods or abstain from sexual activity while treated with carfilzomib and for 90 days after treatment.

Breastfeeding/Lactation
	
Breastfeeding women and women planning on breastfeeding may not participate in the clinical trial

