
Hepatitis B reactivation
	
Carriers of HBV who require treatment with Kyprolis should be closely monitored for signs and symptoms of active HBV infection throughout treatment. Any subject who becomes HBV DNA positive or develops reactivation of HBV should have carfilzomib treatment interrupted and receive appropriate anti-viral treatment as per a specialist in Hepatitis B.

Progressive Multifocal Leukoencephalopathy
	
Patients should be monitored for any new or worsening neurologic, cognitive or behavioral signs or symptoms that may be suggestive of PML as part of the differential diagnosis of CNS disorders. If PML is suspected, patients should be promptly referred to a specialist and appropriate diagnostic testing should be initiated. Discontinue Kyprolis if PML diagnosis is confirmed.

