### **Treatment Discontinuation**

Administration of isatuximab, carfilzomib, lenalidomide and dexamethasone can be discontinued permanently in the event of a treatment-related toxicity at the Treating Investigator's discretion.

If a delay of starting a new cycle is greater than 21 days, the subject should be discontinued from treatment, unless continuing treatment is mutually agreed upon by the Treating Investigator and the Lead Principal Investigator.

If isatuximab, carfilzomib, or lenalidomide requires permanent discontinuation before Cycle 4 induction, the subject's treatment will be discontinued at the end of Cycle 4 induction. If isatuximab, carfilzomib or lenalidomide requires permanent discontinuation during maintenance cycles, the subject may remain on study with the remaining drug(s). Dexamethasone may be discontinued without the subject discontinuing study treatment.

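### Table 10 sets rules for hepatitis B carriers and for HBV DNA, but no hepatitis B test is scheduled to identify carriers before the first dose

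*Combined protocol and SAP*

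**What the plan says.** **Hepatitis B.** The hepatitis B row of Table 10 (Section 6.1) has two parts. For carriers: "Carriers of HBV who require treatment with Kyprolis should be closely monitored for signs and symptoms of active HBV infection throughout treatment". For everyone: "Any subject who becomes HBV DNA positive or develops reactivation of HBV should have carfilzomib treatment interrupted", followed by antiviral treatment as a hepatitis B specialist advises.

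Eligibility is based on history. Exclusion 9 (Section 3.2) covers a subject "known to have active hepatitis B or hepatitis C". The protocol does not say what separates active hepatitis B, which is excluded, from carrier status, which Table 10 expects to meet in the trial.

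No row or footnote of Tables 14A and 14B names HBsAg, anti-HBc or HBV DNA, at screening or later. Footnote 9 lists the chemistry panel, which includes AST, ALT, alkaline phosphatase and bilirubin. Footnote 1 mentions some unnamed pretreatment laboratory values. The antiviral line under permitted therapies in Section 5.4 defers to institutional guidelines and attaches no test.

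**Spirometry.** Exclusion 8 requires FEV1 at screening when COPD or asthma is known or suspected. Footnote 5 of the calendar limits the requirement to subjects who have one of the two conditions and leaves out suspected cases.

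**The concern.** Table 10 gives hepatitis B its own response, different from the general liver rules: interrupt carfilzomib and bring in a specialist for antiviral treatment. To use it, the site must know who is a carrier or must have an HBV DNA result. The calendar supplies neither. If the plan is followed exactly, a carrier whom nobody has identified falls outside the carrier rule. The specific response must then wait until general monitoring raises a question and someone thinks to test for HBV. What is at stake is patient safety, not the efficacy result.

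**Working it through.** No power, alpha or event figure enters this point, so the check compares sections and counts scheduled tests.

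1. **Can carriers enter?** Yes. Exclusion 9 needs disease that is both known and active. An inactive or unrecognised carrier meets neither condition, and Table 10 provides for carriers on treatment.

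2. **Scheduled hepatitis B tests** (Tables 14A and 14B, all rows, and footnotes 1 to 18): 0. This includes known carriers, for whom no serial HBV DNA is set.

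3. **Scheduled chemistry draws with liver tests, on treatment and before maintenance:**
   - Transplant (Table 14A): Cycles 1–2, 2 × 4 = 8; Cycles 3–4, 2 × 2 = 4; Cycles 5–6, 2 × 2 = 4; total 16.
   - Deferred (Table 14B): Cycles 1–2, 2 × 4 = 8; Cycles 3–8, 6 × 2 = 12; total 20.

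   General liver monitoring is therefore frequent.

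4. **Do the liver rules reach HBV?**
   - Table 9 holds drug at Grade 3 or worse liver changes. It then allows the same or a reduced dose and asks for no work-up of cause.
   - Table 10's mild-to-moderate rule needs two consecutive values at least 28 days apart, and then says: "Dose may be re-escalated if liver function tests return to normal and drug-induced hepatotoxicity is excluded". Its hold rule reads: "Resume with a 25% dose reduction if drug-induced hepatotoxicity is excluded". Both conditions prompt a search for cause, but neither names HBV.
   - Section 5.2 delays a new cycle until this is met: "Any other lenalidomide, carfilzomib, or isatuximab-related adverse event that may have occurred has resolved to <Grade 2". It depends on attribution to a study drug.
   - Under Treatment Discontinuation, the agents "can be discontinued permanently in the event of a treatment-related toxicity at the" treating investigator's discretion.

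   The hepatic rules respond to liver abnormality once it appears. An HBV DNA result need not wait for that.

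5. **Could a later step supply the test?** Section 5.1 states: "All subjects will perform stem cell collection after 4 cycles of therapy". Collection follows institutional and FACT guidelines, which are not in the documents. If a site tests then, the carfilzomib doses already scheduled are 3 per cycle × 4 cycles = 12.

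6. **Spirometry.** Exclusion 8 covers known or suspected disease, and footnote 5 covers only subjects with the disease. The two differ, but exclusion 8 governs eligibility, and Section 4.1 has an investigator confirm eligibility at registration, before therapy.

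**The case against.** The strongest reply is that response on suspicion is the visible design of Table 10. Its rows for PRES, TMA and PML also rest on suspicion followed by work-up, with no scheduled test. The hepatitis B row speaks of signs and symptoms. Its trigger is either a positive DNA result or clinical reactivation, and it promises no serial testing. Exclusion 9 treats HIV, hepatitis B and hepatitis C alike as matters of history. Sites may already screen under local practice.

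Much of this stands. The missing calendar row does not contradict Table 10; it leaves part of it without a means of application. A reader might infer that unrecognised carriers have only liver chemistry to protect them, and the documents do not support that. Section 3.1 caps AST and ALT at 2.5 × ULN and bilirubin at 2.0 × ULN at entry. Exclusion 10 covers active systemic infection. Physical examination and adverse event evaluation are scheduled in every drug-treatment phase. The isatuximab safety text in Section 7 allows for tests when clinically indicated.

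The reply does not remove the gap. PRES, TMA and PML are events to be recognised when they occur. Carrier status is a baseline condition to which Table 10 attaches monitoring throughout treatment. For another baseline risk, tumor lysis syndrome, Section 6.1 does ask that high-risk subjects be identified at screening. Local practice may fill the gap, but the documents do not say that it does.

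**Conclusion.** The point holds as an inexpensive safety improvement. The plan schedules 0 hepatitis B tests. The carrier rule therefore reaches only carriers who are already known, and the DNA trigger depends on for-cause testing. The general safeguards are real, but none identifies HBV status.

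Certainty is high that the test is absent. The clinical consequence cannot be sized: the documents give no prevalence, reactivation rate or expected delay, and no number of affected patients is claimed. The primary analysis and sample size are unaffected.

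Two stronger readings should be avoided. First, the documents do not establish that any detectable HBV DNA counts as active disease under exclusion 9, nor do they imply a particular retest interval; both are for the sponsor to set. Second, the spirometry mismatch might look like a way for ineligible patients to enter. It is not, because exclusion 8 controls. It is an editorial matter and adds no weight to the hepatitis B point.

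**What to change.** **Hepatitis B.**
- Add HBsAg and anti-HBc to the existing screening draw in Tables 14A and 14B, with HBV DNA if either is positive, so that carriers are identified before the first dose and Table 10 can be applied.
- Have the sponsor state a repeat HBV DNA interval for identified carriers while they receive carfilzomib.
- Have the sponsor state how a positive DNA result bears on exclusion 9.

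**Cost.** One serology panel per screened patient: at least 50, plus screen failures, with no added visit. A seropositive patient may have to wait for one HBV DNA result within the 28-day screening window. Depending on the sponsor's ruling on exclusion 9, a patient with a positive result might not enrol.

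Repeat assays depend on the interval chosen. For scale only, suppose testing at screening and on Day 1 of every second cycle from Cycle 3. Before maintenance that is 1 + 2 = 3 assays per carrier on the transplant path (Cycles 3, 5) and 1 + 3 = 4 if transplant is deferred (Cycles 3, 5, 7). Assuming 0 to 5 carriers among 50, the total is 0 to 5 × 4 = 20. There is no fixed upper limit after that, because high-risk carfilzomib maintenance runs until progression or unacceptable toxicity. Standard-risk maintenance contains no carfilzomib, so repeats would stop there.

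**Spirometry (separate, editorial).** Make footnote 5 cover known or suspected COPD or asthma, to match exclusion 8. The cost is one phrase.

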### **Tumor Lysis Syndrome**

Tumor lysis syndrome (TLS), which may be associated with multi-organ failure, has been observed in Cycles 1 and 2 of some subjects with multiple myeloma treated with carfilzomib. In addition, MM subjects with high tumor burden (e.g., Durie-Salmon or International Staging System (ISS) Stage II/III) or rapidly increasing M-protein or light chains or compromised renal function glomerular filtration rate (GFR) < 50 mL/min) should be considered to be at particularly high risk. All such subjects should be identified at screening.

During Cycles 1 and 2, serum electrolytes and chemistries are closely monitored. Subjects with laboratory abnormalities consistent with lysis of tumor cells (e.g., serum creatinine  $\geq$  50% increase, lactate dehydrogenase (LDH)  $\geq$  2-fold increase, uric acid  $\geq$  50% increase, phosphate  $\geq$  50% increase, potassium  $\geq$  30% increase, calcium  $\geq$  20% decrease) prior to dosing should not receive the scheduled dose. Subjects with such abnormalities should be re-evaluated as clinically indicated. The Lead Principal Investigator should be consulted if there are further delays. Subjects should be informed of signs and symptoms that may be indicative of TLS such as fevers, chills/rigors, nausea, vomiting, muscle tetany, weakness, or cramping, seizures, and decreased urine output; subjects should be instructed to report such symptoms immediately and seek medical attention.

### **Grade 3 or 4 Adverse Events**

For other Grade 3 or 4 toxicities judged by the investigator to be related to lenalidomide alone, treatment with lenalidomide should be interrupted and restarted at the next lower dose level once the toxicity has resolved to Grade 2 or less. If a Grade 3 toxicity can be controlled (eg, a Grade 3 electrolyte disturbance that can be controlled with repletion within 24 hours), the investigator should discuss the toxicity with the sponsor's medical monitor before interrupting or lowering the lenalidomide dose. Treatment with isatuximab, carfilzomib, and dexamethasone may continue, as applicable depending on the study phase.

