
Pulmonary Toxicities: Interstitial Lung Disease (inc. pneumonitis), Acute Respiratory Failure, and Adult Respiratory Distress Syndrome (ARDS), cough and cough with phlegm
	
NA
	
≥ Grade 2 for Pneumonitis ≥ Grade 3 for ARDS ≥ Grade 4 for Respiratory Failure
 
Carfilzomib attribution, hold drug until resolved to ≤Grade 1. Resume at one level dose reduction

Blood clot in the lungs, fluid in the lungs, bleeding in the lungs
	
NA
	
≥ Grade 3: Carfilzomib attribution, hold drug until resolved to ≤ Grade 1. Resume at one level dose reduction

Gastrointestinal Perforation
	
NA
	
≥ Grade 3: Carfilzomib attribution, hold drug until resolved to Grade 1. Resume at one level dose reduction

Hepatic Toxicities (<math>\geq</math> Grade 3 elevation of AST or ALT, Bilirubin, or other <math>\geq</math> Grade 3 liver abnormalities)	Hold drug until resolved to $\leq$ Grade 1 or baseline. Resume at the same dose or reduced dose as appropriate. If tolerated, the reduced dose may be escalated to the previous dose at the discretion of the physician. Frequent monitoring of liver function should then be implemented.	Hold drug until resolved to $\leq$ Grade 1 or baseline. Resume at the same dose or reduced dose as appropriate. If tolerated, the reduced dose may be escalated to the previous dose at the discretion of the physician. Frequent monitoring of liver function should then be implemented. Please see additional information on hepatic impairment in Table 9
Other non-hematologic toxicity assessed as lenalidomide-related <math>\geq</math> Grade 3	Hold lenalidomide dose. Follow at least weekly. If the toxicity $\leq$ Grade 1 before Day 21 of the current cycle, restart at 1 dose decrement and continue until Day 21 of the current cycle	Full dose
Other non-hematologic toxicity assessed as carfilzomib-related	Full dose	Hold carfilzomib dose until toxicity resolves to $\leq$ Grade 1 or baseline. Restart at 1 dose decrement
Other non-hematologic toxicity assessed as drug-related <math>\geq</math> Grade 3	Hold treatment and restart at 1 dose decrement when toxicity has resolved to $\leq$ Grade 1 or baseline	Hold treatment and restart at 1 dose decrement when toxicity has resolved to $\leq$ Grade 1 or baseline

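### For other non-hematologic Grade 3 or 4 toxicity due to lenalidomide alone, the Section 6.1 text allows restart at Grade 2, while Table 9 and the Section 5.2 Day 1 criterion do not

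*Combined protocol and SAP*

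**What the plan says.** Three places in the protocol bear on restarting lenalidomide after a serious toxicity that has no rule of its own.

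- **Section 6.1, paragraph on Grade 3 or 4 adverse events.** Its scope is given as "For other Grade 3 or 4 toxicities judged by the investigator to be related to lenalidomide alone". Lenalidomide is stopped for the time being and resumed one dose level down "once the toxicity has resolved to Grade 2 or less". No time limit is attached, and the paragraph adds that the other three drugs may continue.
- **Section 6.1, Table 9.** Near its end is a catch-all row, "Other non-hematologic toxicity assessed as lenalidomide-related", for Grade 3 or higher. Lenalidomide is held and followed at least weekly. The restart condition is "If the toxicity $\leq$ Grade 1 before Day 21 of the current cycle, restart at 1 dose decrement". A later row, for other non-hematologic toxicity of Grade 3 or higher that is simply drug-related, reads "Hold treatment and restart at 1 dose decrement when toxicity has resolved to $\leq$ Grade 1 or baseline".
- **Section 5.2, Pre-Treatment Criteria.** A new cycle may begin on Day 1 only if certain conditions are met. One is that any other lenalidomide, carfilzomib or "isatuximab-related adverse event that may have occurred has resolved to <Grade 2". Lenalidomide-related allergic reactions and cardiac arrhythmias have a separate, stricter condition there.

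**The concern.** The Section 6.1 paragraph and the Table 9 row appear to cover the same events and give different grades for restart. Investigators following different parts of the same section could treat the same patient differently, each with support in the protocol.

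This is a safety rule for one of the regimen's main drugs. Section 12.1 also plans summaries of dose reductions and of adverse events leading to dose reduction or interruption. If two rules are in use, those summaries mix patients held to different conditions, and a deviation from the restart rule cannot be judged consistently.

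**Working it through.** No arithmetic applies. The check asks whether the rules cover the same events, and at which grades they disagree.

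**Step 1: Do the scopes overlap?** The paragraph covers Grade 3 or 4 events related to lenalidomide alone and is not limited by organ system. The Table 9 row covers Grade 3 or higher, lenalidomide-related, non-hematologic events not named elsewhere in the table. The paragraph's own example is "a Grade 3 electrolyte disturbance that can be controlled with repletion within 24 hours", a non-hematologic event without a Table 9 row. The common ground is therefore an event that is:

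- Grade 3 or 4,
- non-hematologic,
- judged related to lenalidomide alone, and
- without its own Table 9 row.

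This excludes, among others, thrombocytopenia, neutropenia, rash, arrhythmia, allergy, infection, neuropathy, renal dysfunction, thrombosis, thyroid disorders, heart failure and hepatic toxicity.

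**Step 2: Do they agree on the dose?** Yes. Both resume one level lower.

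**Step 3: Do they agree on the grade?** For an event in the overlap, by its current grade:

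| Current grade | Section 6.1 paragraph | Table 9 catch-all row (before Day 21) | Section 5.2 (Day 1 of next cycle) |
|---|---|---|---|
| 3 or higher | hold | hold | new cycle not started |
| 2 | restart | hold | new cycle not started |
| 1 or less | restart | restart | this criterion is met |

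The disagreement is confined to Grade 2, so the thresholds differ by one full grade.

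**Step 4: Does timing separate the rules?** The Table 9 row governs restart within the current cycle, and Section 5.2 governs the start of the next. They are different decisions and would not normally apply at the same moment. The paragraph has no time limit and so meets both. Applied mid-cycle it contradicts Table 9; applied at Day 1 it contradicts Section 5.2. In addition, the Table 9 row is silent on what happens if Grade 1 is not reached before Day 21.

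**Step 5: Is precedence stated?** No. Section 5.2 points to Table 9 in Section 6.1 for changes within a cycle, but the paragraph is also in Section 6.1 and neither defers to the other. The Table 9 entries are headed as recommendations and the paragraph uses *should*, so the force of the wording does not rank them.

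**The case against.** The best defence is that the word *other* makes the paragraph a residual rule for events outside Table 9. That would work if the table had no residual row. It has one for the same drug and grades, and the electrolyte example falls within it.

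A second defence is that the practical difference is small. Much of this stands. Both rules interrupt lenalidomide and resume it one level lower; they differ only in when. If Section 5.2 is followed at the next Day 1, the extra exposure under the paragraph is limited to the dosing days left in one Day 1–21 course.

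Three stronger readings are tempting, and the documents do not support them.

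- A reader might infer that every patient with residual Grade 2 lenalidomide-related toxicity is affected. The event must first have been Grade 3 or 4 and must meet all the conditions in Step 1. In a four-drug regimen, attribution to lenalidomide alone narrows the group further.
- A reader might infer that the conflict disturbs the primary endpoint, because it can alter exposure during the four cycles before response is assessed. Nothing in the documents shows an effect on the complete response rate, and no frequency is given from which to estimate one.
- A reader might infer that one threshold should apply throughout. The protocol sets thresholds by event: the neuropathy row uses Grade 2 or less, and Section 5.2 uses below Grade 1 for lenalidomide-related allergy and arrhythmia. Those differences are not part of this contradiction.

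**Conclusion.** The contradiction is real and narrow. Within the group defined in Step 1, a patient whose toxicity has improved only to Grade 2 is restarted under the Section 6.1 paragraph, held in-cycle under the Table 9 catch-all row, and held at Day 1 under Section 5.2.

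The number of patients affected cannot be computed. The sample size, the exact binomial test and its rejection limits do not depend on this rule. The consequence is inconsistent application of a safety rule, and dose-modification summaries that may combine two practices.

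The conclusion assumes that *other* in the paragraph does not exclude events covered by the Table 9 catch-all row; the paragraph's own example supports that reading. No view is taken on which threshold is right.

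**What to change.** Reconcile the Section 6.1 paragraph on Grade 3 or 4 adverse events with the Table 9 row for other non-hematologic lenalidomide-related toxicity. The revised text should state:

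- which of the two prevails, or a single condition given in both;
- how that condition relates to the Day 1 criterion in Section 5.2; and
- what applies when the condition is not met before Day 21.

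Leave the event-specific rules, such as those for neuropathy, allergy and arrhythmia, as they are. The clinical team decides the threshold.

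The cost is protocol wording only. No change to sample size, endpoints or analysis methods is needed.
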